**Table ITPStat2**

**Statistical Comparisons of Plasma Nicotine Pharmacokinetic Parameter Tmax for THS and CIG (PK Population)**

Comparison	Parameter	Difference <X> - <Y>		
		Median	95% Confidence Interval	p-value
P1R vs CIG	Tmax	X.XX	X.XX-X.XX	X.XXXX
P1M vs CIG	Tmax	X.XX	X.XX-X.XX	X.XXXX
P1R: <> P1M: <> CIG: <>				
The difference between products (product effect) and the 95% confidence interval for the difference was calculated using Hedges-Lehmann estimator.				
Source: Table 14.2.1.8				

**Notes for Generating the Actual Table:**

Presentation of Data:

- Median difference will be presented to 2 decimals or 3 significant figures
- 95% CI will be presented to 4 decimals
- p-value will be presented to 4 decimals

Programming notes: The following comparisons will be included in the table: P1R versus CIG and P1M versus CIG.

If there is at least a difference of 1 subject between the Randomized and PK populations, a column for population will be added as the first column and the summary statistics will be presented for each population with table title updated to reflect the populations used in the analysis.

Philip Morris Products S.A.  
 THS Induction device and regular or menthol sticks, P1-PK-12  
 [REDACTED]  
 CA39924

---

In-text Shell ITPDSum1 will be in the following RFT format:

**Table ITPDSum1 Summary of VAS Craving Assessment (PK Population)**

Time Point	THS regular stick (P1R)	THS menthol stick (P1M)	Combustible Cigarette (CIG)
Tv0: Within 15 minutes prior to T0	XXX.X (XX.X) [n=xx]	XXX.X (XX.X) [n=xx]	XXX.X (XX.X) [n=xx]
Tv1 after 4 minutes	XXX.X (XX.X) [n=xx]	XXX.X (XX.X) [n=xx]	XXX.X (XX.X) [n=xx]
Tv2 after 10 minutes	XXX.X (XX.X) [n=xx]	XXX.X (XX.X) [n=xx]	XXX.X (XX.X) [n=xx]
Tv3 after 15 minutes	XXX.X (XX.X) [n=xx]	XXX.X (XX.X) [n=xx]	XXX.X (XX.X) [n=xx]
Tv4 after 30 minutes	XXX.X (XX.X) [n=xx]	XXX.X (XX.X) [n=xx]	XXX.X (XX.X) [n=xx]
Tv5 after 10 hours	XXX.X (XX.X) [n=xx]	XXX.X (XX.X) [n=xx]	XXX.X (XX.X) [n=xx]

Values are presented as arithmetic mean ( $\pm$  SD).  
 Source: Tables <XXXX> and <YYYY>

Programmer Note: If there is at least a difference of 1 subject between the Randomized and PK populations, a column for population will be added as the first column and the summary statistics will be presented for each population with table title updated to reflect the populations used in the analysis.

Philip Morris Products S.A.  
 THS Induction device and regular or menthol sticks, P1-PK-12  
 [REDACTED]  
 CA39924

---

In-text Shell ITPDSum2 will be in the following RFT format:

**Table ITPDSum2 Summary of VAS Liking Assessment (PK Population)**

Time Point	THS regular stick (P1R)	THS menthol stick (P1M)	Combustible cigarette (CIG)
Tv3 after 15 minutes	XXX.X (XX.X) [n=xx]	XXX.X (XX.X) [n=xx]	XXX.X (XX.X) [n=xx]

Values are presented as arithmetic mean ( $\pm$  SD).  
 Source: Tables <XXXX> and <YYYY>

Programmer Note: If there is at least a difference of 1 subject between the Randomized and PK populations, a column for population will be added as the first column and the summary statistics will be presented for each population with table title updated to reflect the populations used in the analysis.

Philip Morris Products S.A.  
 THS Induction device and regular or menthol sticks, P1-PK-12  
 [REDACTED] CA39924

---

In-text Shell IAEQ will be in the following RFT format:

**Table IAEQ Overall Product Use Emergent Adverse Events (Safety Population)**

Adverse Event	Admission (N=X)	Product Administration				SFU (N = X)
		P1R (N = X)	P1M (N-X)	CIG (N = X)	Overall (N = X)	
Number of Subjects With PUEAEs	XX (XX%)	XX (XX%)	XX (XX%)	XX (XX%)	XX (XX%)	XX (XX%)
Number of Subjects With SAEs	XX (XX%)	XX (XX%)	XX (XX%)	XX (XX%)	XX (XX%)	XX (XX%)
Number of Subjects With IP Events	XX (XX%)	XX (XX%)	XX (XX%)	XX (XX%)	XX (XX%)	XX (XX%)
Number of Subjects With AEs Leading to Discontinuation	XX (XX%)	XX (XX%)	XX (XX%)	XX (XX%)	XX (XX%)	XX (XX%)
Number of Subjects With AEs Leading to Death	XX (XX%)	XX (XX%)	XX (XX%)	XX (XX%)	XX (XX%)	XX (XX%)
Number of Subjects With AEs Related to IP	XX (XX%)	XX (XX%)	XX (XX%)	XX (XX%)	XX (XX%)	XX (XX%)

P1R: THS regular stick  
 P1M: THS menthol stick  
 CIG: Combustible cigarette  
 Although a subject may have had 2 or more adverse events, the subject is counted only once within a category. The same subject may appear in different categories.  
 PUEAEs = Product use-emergent adverse events; SAEs = Serious adverse events; IP = Investigational product  
 Admission = after ICF and prior to the product test on Day 1  
 SFU = after discharge from CRU to safety follow-up visit  
 Source: Table 14.3.1.1  
 Program: /CAXXXX/sas\_prg/stsas/intext/t\_ae.sas DDMMYYYY HH:MM

Philip Morris Products S.A.  
 THS Induction device and regular or menthol sticks, P1-PK-12  
 [REDACTED] CA39924

In-text Shell IAES will be in the following RFT format:

**Table IAES Summary of Adverse Events by System Organ Class and Preferred Term (Safety Population)**

Adverse Event	Admission (N=X)	Product				SFU (N = X)
		P1R (N = X)	P1M (N-X)	CIG (N = X)	Overall (N = X)	
Number of Subjects With PUEAEs	XX (XX%)	XX (XX%)	XX (XX%)	XX (XX%)	XX (XX%)	XX (XX%)
Number of Subjects Without PUEAEs	XX (XX%)	XX (XX%)	XX (XX%)	XX (XX%)	XX (XX%)	XX (XX%)
Eye disorders	XX (XX%)	XX (XX%)	XX (XX%)	XX (XX%)	XX (XX%)	XX (XX%)
Visual blurred	XX (XX%)	XX (XX%)	XX (XX%)	XX (XX%)	XX (XX%)	XX (XX%)
Gastrointestinal disorders	XX (XX%)	XX (XX%)	XX (XX%)	XX (XX%)	XX (XX%)	XX (XX%)
Dyspepsia	XX (XX%)	XX (XX%)	XX (XX%)	XX (XX%)	XX (XX%)	XX (XX%)
Nausea	XX (XX%)	XX (XX%)	XX (XX%)	XX (XX%)	XX (XX%)	XX (XX%)
Musculoskeletal and connective tissue disorders	XX (XX%)	XX (XX%)	XX (XX%)	XX (XX%)	XX (XX%)	XX (XX%)
Back pain	XX (XX%)	XX (XX%)	XX (XX%)	XX (XX%)	XX (XX%)	XX (XX%)
Muscle cramps	XX (XX%)	XX (XX%)	XX (XX%)	XX (XX%)	XX (XX%)	XX (XX%)
Musculoskeletal pain	XX (XX%)	XX (XX%)	XX (XX%)	XX (XX%)	XX (XX%)	XX (XX%)
Nervous system disorders	XX (XX%)	XX (XX%)	XX (XX%)	XX (XX%)	XX (XX%)	XX (XX%)
Headache	XX (XX%)	XX (XX%)	XX (XX%)	XX (XX%)	XX (XX%)	XX (XX%)
Reproductive system and breast disorders	XX (XX%)	XX (XX%)	XX (XX%)	XX (XX%)	XX (XX%)	XX (XX%)
Vaginal discharge	XX (XX%)	XX (XX%)	XX (XX%)	XX (XX%)	XX (XX%)	XX (XX%)
Respiratory, thoracic and mediastinal disorders	XX (XX%)	XX (XX%)	XX (XX%)	XX (XX%)	XX (XX%)	XX (XX%)
Epistaxis	XX (XX%)	XX (XX%)	XX (XX%)	XX (XX%)	XX (XX%)	XX (XX%)
Skin and subcutaneous tissue disorders	XX (XX%)	XX (XX%)	XX (XX%)	XX (XX%)	XX (XX%)	XX (XX%)
Sweating increased	XX (XX%)	XX (XX%)	XX (XX%)	XX (XX%)	XX (XX%)	XX (XX%)

[figure not shown]
P1R: THS regular stick  
 P1M: THS menthol stick  
 CIG: Combustible cigarette  
 Although a subject may have had 2 or more adverse events, the subject is counted only once within a category. The same subject may appear in different categories.  
 Adverse events are classified according to MedDRA Version 25.1.  
 PUEAEs = Product use-emergent adverse events  
 Admission = after ICF and prior to the product test on Day 1  
 SFU = after discharge from CRU to safety follow-up visit  
 Source: Table 14.3.1.2  
 Program: /CAXXXX/sas\_prg/stsas/intext/t\_ae.sas DDMMMYYYY HH:MM

Philip Morris Products S.A.  
 THS Induction device and regular or menthol sticks, P1-PK-12  
 [REDACTED] CA39924

## 12.2 Figures Shells

Figures PFPConc2 (both in-text and post-text) will be in the following RFT format:

Figure Mean Plasma Nicotine Concentrations Versus Time (Linear Scale) (PK Population)

[figure not shown]
Program: /CAXXXXX/sas\_prg/pksas/adam\_meangraph.sas DDMMYY HH:MM  
 Program: /CAXXXXX/sas\_prg/pksas/meangraph.sas DDMMYY HH:MM

Programming note : the legend will present the 3 products 'Product X: Product Description'  
 The x-axis title will be: 'Time From Start of Product Use (min)'.

Philip Morris Products S.A.  
 THS Induction device and regular or menthol sticks, P1-PK-12  
 [REDACTED] CA39924

Figure PFPCconc1 will be in the following RFT format:

Figure Mean (SD) Plasma Nicotine Concentrations Versus Time (Linear Scale) (PK Population)

[figure not shown]

Programming note : the legend will present the 3 products 'Product X: Product Description'  
 The x-axis title will be: 'Time From Start of Product Use (min)'.

Philip Morris Products S.A.  
 THS Induction device and regular or menthol sticks, P1-PK-12  
 [REDACTED] CA39924

Figure PFPCconc3 will be in the following RFT format :

Figure Mean Plasma Nicotine Concentrations Versus Time (Semi-Log Scale) (PK Population)

Program: /CAXXXXX/sas\_prg/pksas/adam\_meangraph.sas DDMMYY HH:MM  
 Program: /CAXXXXX/sas\_prg/pksas/meangraph.sas DDMMYY HH:MM

[figure not shown]
Programming note : the legend will present the 3 products 'Time From Start of Product Use (min)'  
 The x-axis title will be: 'Time From Start of Product Use (min)'

Philip Morris Products S.A.  
 THS Induction device and regular or menthol sticks, P1-PK-12  
 [REDACTED]  
 CA39924

**Linear and Semi-log Figures in Appendix 16.2.6.1 will have the following format:**

Appendix 16.2.6.1

Individual Plasma Nicotine Concentrations Versus Time (Linear and Semi-Log Scales)

Program: /CAXXXXX/sas\_prg/pksas/adam\_indgraph.sas DDMMYYYY HH:MM  
 Program: /CAXXXXX/sas\_prg/pksas/indgraph-all.sas DDMMYYYY HH:MM

Programming note : the legend will present the 3 products.  
 The x-axis title will be: 'Time From Start of Product Use (min)'  
 The y-axis title will be: 'Plasma Nicotine Concentration (ng/mL)'

Philip Morris Products S.A.  
 THS Induction device and regular or menthol sticks, P1-PK-12  
 [REDACTED] CA39924

---

### 12.3 Section 14 Summary Tables Shells

Page 1 of X

Table CDS Disposition Summary (Safety Population)

Category	Overall
Screened	XXX
Enrolled	XX
Enrolled and Exposure to P1 Product	XX
Randomized	XX (100%)
Completed Study	XX ( XX%)
Discontinued From Study	X ( XX%)
<Reason>	X ( XX%)

Program: /CAXXXX/sas\_prg/stsas/tab/programname2022Q1programname2022Q1.sas DDMMYYYY HH:MM

Philip Morris Products S.A.  
 THS Induction device and regular or menthol sticks, P1-PK-12  
 [REDACTED] CA39924

Page 1 of X

Table SDS Subject Product Use Status and Study Disposition (Safety Population) (Safety Population)

Subject Number	Randomized Product Sequence	Product Administrated			Study Completion	
		P1R	P1M	CIG	Status	Date
X	XXXXXXXXXX	Yes	No	Yes	Discontinued From Study: <Reason>	DDMONYYYY
X	XXXXXXXXXX	Yes	Yes	Yes	Completed Study	DDMONYYYY
X	XXXXXXXXXX	Yes	Yes	Yes	Completed Study	DDMONYYYY
X	XXXXXXXXXX	Yes	Yes	Yes	Completed Study	DDMONYYYY
		XX	XX	XX		

Programmer Note: Please refer to Section 5 for the product description.

P1R: < >

P1M: < >

CIG: < >

Program: /CAXXXX/sas\_prg/stsas/tab/programname2022Q1.sas DDMMYYYY HH:MM

Philip Morris Products S.A.

THS Induction device and regular or menthol sticks, P1-PK-12

CA39924

Page 1 of X

Table CDEM Demographic Summary (Safety Population)

Sex	Trait	Category/Statistic	Overall
All	Sex	Male	X (XX%)
		Female	X (XX%)
Race		Asian	X (XX%)
		Black or African American	X (XX%)
		White	X (XX%)
Ethnicity		Hispanic or Latino	X (XX%)
		Not Hispanic or Latino	X (XX%)
Age (yr)		n	X
		Mean	X.X
		SD	X.XX
		Minimum	XX
		Median	X.X
		Maximum	XX
Body Mass Index (kg/m  )		n	X
		Mean	X.X
		SD	X.XX
		Minimum	XX
		Median	X.X
		Maximum	XX

Descriptive statistics for body mass index, height, and weight are calculated using screening measurements.

Program: /CAXXXX/sas\_prg/stsas/tab/programname2022Q1.sas DDMMYYYY HH:MM

Programmer note: If there is at least a difference of 1 subject between the safety, Randomized, and PK, and populations, a column for population will be added as the first column and the summary statistics will be presented for each population with table title updated to reflect the populations used in the analysis. The summarization for each sex will also be presented.

Philip Morris Products S.A.  
 THS Induction device and regular or menthol sticks, P1-PK-12  
 [REDACTED] CA39924

Page 1 of X

Table CUB Tobacco/Nicotine-Containing Product Use History Summary (Safety and PK Population)

Sex	Question	Product	Answer	Overall
All	Have you smoked continuously for the past 3 years?	Manufactured or roll-your-own cigarettes	Yes No	X (XX.X%) X (XX.X%)
		Cigars/cigarillos	Yes No	X (XX.X%) X (XX.X%)
		XXXXXXX		
All	In the last 4 weeks, on average how many of these products did you smoke/use per day?	Manufactured or roll-your-own cigarettes	1 cigarette or less 2 to 5 cigarettes 6 to 9 cigarettes 10 to 19 cigarettes 1 to 2 packs More than 2 packs	X (XX.X%) X (XX.X%) X (XX.X%) X (XX.X%) X (XX.X%) X (XX.X%)
	Do you plan to quit smoking cigarettes within the next 3 months?		Yes No	X (XX.X%) X (XX.X%)
	Do you plan to stop using tobacco and/or nicotine containing products within the next 3 months?		Yes No	X (XX.X%) X (XX.X%)

Program: /CAXXXX/sas\_prg/stsas//tab/ADaM\_program\_name.sas DDMMYYYY HH:MM

Programmer Note: All products (Manufactured or roll-your-own cigarettes, Cigars/cigarillos, Tobacco Pipe, Smokeless tobacco products, E-vapour products), and Nicotine replacement therapy (NRT) products in the tobacco/nicotine use history will be included in the descriptive statistics table. Number of years smoked will be presented using descriptive statistics. If there is at least a difference of 1 subject between the safety, Randomized, and PK, and populations, a column for population will be added as the first column and the summary statistics will be presented for each population with table title updated to reflect the populations used in the analysis. The summarization for each sex will also be presented.

Philip Morris Products S.A.

THS Induction device and regular or menthol sticks, P1-PK-12

CA39924

Page 1 of X

Table CSU Usual Brand Cigarettes Summary (Safety and PK Population)

Sex	Trait	Category/Statistic	Overall
All	Substance	XXXXX XXXXXXXXXX	X (XX%) X (XX%)
	Amount	n Mean SD Minimum Median Maximum	X X.X X.XX XX X.X XX
	Brand	XXXXXXXXXX XXXXXXXXXXXXXXXXXXXXXX XXXXX	X (XX%) X (XX%) X (XX%)
	Brand Style	XXXXXXX XXXXXXXXXXXXXXXXXXXXXX	X (XX%) X (XX%)
	Flavour	XXXXXXX XXXXXXXXXXXXXXXXXXXXXX	X (XX%) X (XX%)
	Cigarette Length	XXXXXXX XXXXXXXXXXXXXXXXXXXXXX	X (XX%) X (XX%)

Program: /CAXXXX/sas\_prg/stsas/tab/programname2022Q1.sas DDMMYYYY HH:MM

Programmer note: If there is at least a difference of 1 subject between the safety, Randomized, and PK, and populations, a column for population will be added as the first column and the summary statistics will be presented for each population with table title updated to reflect the populations used in the analysis. The summarization for each sex will also be presented.

Philip Morris Products S.A.  
 THS Induction device and regular or menthol sticks, P1-PK-12  
 [REDACTED] CA39924

Page 1 of X

Table CFT Fagerström Test for Nicotine Dependence Summary (Safety and PK Population)

Sex	Trait	Category/Statistic	Overall
All	Fagerstrom Score	n	X
		Mean	X.X
	SD		X.XX
		Minimum	XX
		Median	X.X
		Maximum	XX
	Nicotine Dependence Level	Mild (0-3)	X (XX%)
		Moderate (4-6)	X (XX%)
		Severe (7-10)	X (XX%)

Program: /CAXXXX/ sas\_prg/stsas/tabc/programname2022Q1.sas DDMMYYYY HH:MM

Programmer note: If there is at least a difference of 1 subject between the safety, Randomized, and PK, and populations, a column for population will be added as the first column and the summary statistics will be presented for each population with table title updated to reflect the populations used in the analysis. The summarization for each sex will also be presented.

Philip Morris Products S.A.

THS Induction device and regular or menthol sticks, P1-PK-12

CA39924

**Note: Plasma Nicotine Concentration Tables (CPCONC1) will have the following format:**

Page 1 of X

Table Plasma Nicotine Concentrations (ng/mL) Following THS Regular stick (P1R) (PK Population)

Subject Number	Product Sequence	Sex	Sample Times (minutes)											
			Pre-use	XX										
XX	XXXXXX	X	XX	XX	XX	XX	XX	XX	XX	XX	XX	XX	XX	XX
XX	XXXXXX	X	XX	XX	XX	XX	XX	XX	XX	XX	XX	XX	XX	XX
XX	XXXXXX	X	XX	XX	XX	XX	XX	XX	XX	XX	XX	XX	XX	XX
n		X		X	X	X	X	X	X	X	X	X	X	X
n missing		X		X	X	X	X	X	X	X	X	X	X	X
% n missing		X		X	X	X	X	X	X	X	X	X	X	X
Mean		X.X		X.X										
SD		X.XX		X.XX										
95% CI		X.X-X,X		X.X-X,X										
Minimum		XX		XX										
1st quartile		X.X		X.X										
Median		X.X		X.X										
3rd quartile		X.X		X.X										
Maximum		XX		XX										

Program: /CAXXXX/sas\_prg/pksas/PROGRAMNAME.SAS DDMMYYYY HH:MM

Programming Notes: For the 95% CI (of Mean), the lower and upper limits may be presented on different rows if the space limit requires it. If there is at least a difference of 1 subject between the Randomized and PK populations, a column for population will be added as the first column and the summary statistics will be presented for each population with table title updated to reflect the populations used in the analysis.

The number and percent of values below LLOQ or above ULOQ are to be presented in each summary table. If 50% or more data are below LLOQ or above ULOQ, only the number and percent of values below LLOQ or above ULOQ is to be reported in the summaries, together with minimum (= LLOQ/2) and maximum (= ULOQ) of the observed values.

Footnotes to include under the table, as appropriate:

<. = Concentration value missing or not reportable.>

<Concentration values that were below the limit of quantitation (BLQ) of 0.200 ng/mL were set to one-half of the limit of quantitation for the calculation of summary statistics.>

Sample Times are listed in Section 6.1. Descriptive statistics precision is specified in Section 6.4.

Philip Morris Products S.A.

THS Induction device and regular or menthol sticks, P1-PK-12

CA39924

**Note: Plasma Nicotine Pharmacokinetic Parameter Tables (CPPAR1) will have the following format:**

Page 1 of X

Table Plasma Nicotine Pharmacokinetic Parameters Following THS Regular stick (P1R) (PK Population)

Subject Number	Product Sequence	Sex	Parameters				
			Parm 1 <unit>	Parm 2 <unit>	Parm 3 <unit>	Parm 4 <unit>	Parm X <unit>
XX	XXXXXX	X	X.XX	X.XX	X.XX	X.XX	X.XX
XX	XXXXXX	X	X.XX	X.XX	X.XX	X.XX	X.XX
XX	XXXXXX	X	X.XX	X.XX	X.XX	X.XX	X.XX
<hr/>							
n			X	X	X	X	X
n missing			X	X	X	X	X
% n missing			X	X	X	X	X
Mean			X.X	X.X	X.X	X.X	X.X
SD			X.XX	X.XX	X.XX	X.XX	X.XX
95% CI of Mean			X.XX-XX.XX	(repeat format for other parameters)			
Minimum			XX	XX	XX	XX	XX
1st quartile			X.X	X.X	X.X	X.X	X.X
Median			X.X	X.X	X.X	X.X	X.X
3rd quartile			X.X	X.X	X.X	X.X	X.X
Maximum			XX	XX	XX	XX	XX
Geom. Mean			X.X	X.X	X.X	X.X	X.X
Geom. CV%			XX.X	XX.X	XX.X	XX.X	XX.X
95% CI of Geom. Mean			X.XX-XX.XX	(repeat format for other parameters)			

Program: /CAXXXX/sas\_prg/pksas/PROGRAMNAME.SAS DDMMYY YYYY HH:MM

Programming Notes: Footnote to include under the table, as appropriate: <. = Parameter value missing or not reportable.>

If there is at least a difference of 1 subject between the Randomized and PK populations, a column for population will be added as the first column and the summary statistics will be presented for each population with table title updated to reflect the populations used in the analysis.

The plasma nicotine PK parameters are Cmax (ng/mL), Tmax (min), AUC0-24 (ng\*min/mL), AUC0-Tmax (ng\*min/mL).

Geometric mean, geometric CV% and 95% CI of Geom. Mean will be calculated only for Cmax, AUC0-24, and AUC0-Tmax.

For Tmax, only median, Q1, Q3, minimum and maximum will be presented.

Descriptive statistics precision is specified in Section 6.3.

Philip Morris Products S.A.

THS Induction device and regular or menthol sticks, P1-PK-12

CA39924

**Note: Statistical comparison of PK parameters (CPStat1) will have the following format:**

Page 1 of X

Table Statistical Comparison of Plasma Nicotine Pharmacokinetic Parameters Cmax, AUC0-24, and AUC0-Tmax (PK Population)

Comparison	Parameter	Geometric LS Means		% Geometric LS Mean Ratio (Test/Comparator)	90% Confidence Interval	p-value
		Test (n)	Comparator (n)			
P1R vs CIG	Cmax	X.XX (X)	X.XX (X)	XXX.XX	XX.XX - XXX.XX	X.XXXX
	AUC0-24	X.XX (X)	X.XX (X)	XXX.XX	XX.XX - XXX.XX	X.XXXX
	AUC0-Tmax	X.XX (X)	X.XX (X)	XXX.XX	XX.XX - XXX.XX	X.XXXX
P1M vs CIG	Cmax	X.XX (X)	X.XX (X)	XXX.XX	XX.XX - XXX.XX	X.XXXX
	AUC0-24	X.XX (X)	X.XX (X)	XXX.XX	XX.XX - XXX.XX	X.XXXX
	AUC0-Tmax	X.XX (X)	X.XX (X)	XXX.XX	XX.XX - XXX.XX	X.XXXX

P1R = < >

P1M = < >

CIG = < >

The mixed model includes sequence, period, product as fixed effects and subject as a categorical random effect modeling the within subject correlations.

Parameters are ln-transformed prior to analysis

Geometric least-squares means (LS Means) are calculated by exponentiating the LS Means from the ANOVA.

% Geometric LS Mean Ratio = 100\*(Test/Comparator)

Test = The first product in the comparison

Comparator = The second product in the comparison

n = Number of observation used in the analysis

Program: /CAXXXX/sas\_prg/pksas PROGRAMNAME.SAS DDMMYYYY HH:MM

Programming note: Geometric LS Means to be presented to same precision as Mean in the PK parameter table. Geometric Mean Ratio and 90% confidence intervals will be presented to 2 decimal places; p-value will be presented to 4 decimals.

Philip Morris Products S.A.  
 THS Induction device and regular or menthol sticks, P1-PK-12  
 [REDACTED] CA39924

---

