12.1.4 Significance Level for Inferential Analysis

No significance level will be used. All confidence intervals will be computed at 95%.

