## 6.5 Statistical Analysis of Pharmacokinetic Parameters

### 6.5.1 Main Analysis

A mixed model analysis of variance (ANOVA) will be conducted on Cmax, AUC0-24h, and AUC0-Tmax endpoints in the natural logarithmic scale.

The model will include terms for sequence, period, product as fixed effects and subject as a categorical random effect modeling the within subject correlations.

The ANOVA analysis could be performed using the following SAS code:

```
PROC MIXED data=<> method=REML;
class subject sequence period product;
model log(parameter) = sequence period product/ddf=KR;
repeated product / subject=subject type=csh;
lsmeans product / pdiff=control("CIG") cl alpha=0.05;
RUN;
```

The results of this analysis for each of are presented in terms of geometric least square ratios and 95% confidence intervals for each THS / CIG ratio.

This approach is consistent with the guidelines in the European Medicines Agency's guidelines for bioequivalence investigations and FDA's Center for Drug Evaluation and Research.

The analysis of Tmax will be performed by conducting a Wilcoxon signed rank test and calculating the median Tmax for each product along with the Hodges-Lehmann estimate of the median difference between products, and the related 95% CI.

This analysis could be performed using the following SAS code:

```
PROC NPAR1WAY hl(refclass=<>) alpha=.05 data=<> hl;
class TRT;
var AVAL;
ods output HodgesLehmann=HodgesLehmann;
RUN;
```

Philip Morris Products S.A.  
 THS Induction device and regular or menthol sticks, P1-PK-12  
 [REDACTED] CA39924

---

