## 9. SUMMARY OF CHANGES FROM PROTOCOL-PLANNED ANALYSIS

The analyses described in this SAP are aligned with those analyses described in the protocol.

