#### **14.2.1 Plasma Nicotine Tables**

Number	Title	Shell
Table 14.2.1.1	Plasma Nicotine Concentrations (ng/mL) Following THS Regular stick (P1R) (PK Population)	CPCONC1

Philip Morris Products S.A.  
 THS Induction device and regular or menthol sticks, P1-PK-12  
 [REDACTED] CA39924

Number	Title	Shell
Table 14.2.1.2	Plasma Nicotine Concentrations (ng/mL) Following THS Menthol stick (P1M) (PK Population)	CPCONC1
Table 14.2.1.3	Plasma Nicotine Concentrations (ng/mL) Following Combustible Cigarette (CIG) (PK Population)	CPCONC1
Table 14.2.1.4	Plasma Nicotine Pharmacokinetic Parameters Following THS Regular stick (P1R) (PK Population)	CPPAR1
Table 14.2.1.5	Plasma Nicotine Pharmacokinetic Parameters Following THS Menthol stick (P1M) (PK Population)	CPPAR1
Table 14.2.1.6	Plasma Nicotine Pharmacokinetic Parameters Following Combustible Cigarette (CIG) (PK Population)	CPPAR1
Table 14.2.1.7	Statistical Comparison of Plasma Nicotine Pharmacokinetic Parameters: THS Versus CIG (PK Population)	CPStat1
Table 14.2.1.8	Nonparametric Statistical Comparison of Plasma Nicotine Tmax: THS Versus CIG (PK Population)	CPStat1

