**Table ITPStat1**

**Statistical Comparisons of Plasma Nicotine PK Parameters for THS and CIG  
 (PK Population)**

Parameter	Product <X> (Test)		Product <Y> (Comparator)		GMR (%)	95% Confidence Interval	Intra subject CV%
	Geometric LSMs	n	Geometric LSMs	n			
param1 (units)	XXX.X	XX	XXX.X	XX	XX.XX	XX.XX - XX.XX	X.XX
param2 (units)	XXX.X	XX	XXX.X	XX	XX.XX	XX.XX - XX.XX	X.XX
param3 (units)	XXX.X	XX	XXX.X	XX	XX.XX	XX.XX - XX.XX	X.XX

Product <X>: <Label for Test Product>  
 Product <Y>: <Label for Comparator Product>  
 Geometric least-squares means (LSMs) are calculated by exponentiating the LSMs derived from the ANOVA.  
 Geometric Mean Ratio (GMR) = 100\*(test/comparator)  
 Intra-subject CV% was calculated as 100 x square root(exp[MSE]-1), where MSE = Residual variance from ANOVA.  
 Source: Table 14.2.1.7

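### The Section 14 table shells for the THS/CIG comparisons specify 90% confidence intervals where the protocol and SAP text specify 95%, and the Tmax table is pointed to the wrong shell

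*SAP*

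**What the plan says.** **Places that specify 95%**

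- Protocol section 12.1.4 is a general rule: "No significance level will be used. All confidence intervals will be computed at 95" per cent.
- The protocol synopsis and protocol section 12.4.1.4 repeat 95% for the THS/CIG ratios and for the Tmax difference.
- SAP section 6.5.1 plans "95% confidence intervals for each THS / CIG ratio" and a 95% interval for the Hodges-Lehmann Tmax difference. Alpha is 0.05 in both the PROC MIXED and the PROC NPAR1WAY code.
- In-text shell ITPStat1 has a 95% column and cites "Source: Table 14.2.1.7".
- In-text shell ITPStat2 has a 95% column, the note "95% CI will be presented to 4 decimals", and cites "Source: Table 14.2.1.8".

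**Places that specify 90%**

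- SAP section 12.3, shell CPStat1 (Cmax and the two AUCs), in its column heading and in its programming note: "Geometric Mean Ratio and 90% confidence intervals will be presented to 2 decimal places; p-value will be presented to 4 decimals".
- SAP section 12.3, shell CPStat2 (Tmax), in its column heading and in its presentation note. The programmer's note of the same shell then says 95%.

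**Shell assignment.** In SAP section 11.2, the list of Section 14.2.1 tables gives Table 14.2.1.8, "Nonparametric Statistical Comparison of Plasma Nicotine Tmax: THS Versus CIG (PK Population"), the shell CPStat1, as it does Table 14.2.1.7. No table is assigned CPStat2.

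**Declared changes.** SAP section 9 states: "The analyses described in this SAP are aligned with those analyses described in the protocol".

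**The concern.** The study is descriptive, so the main comparative result is each ratio or median difference together with its interval. Tables 14.2.1.7 and 14.2.1.8 are the tables of record for these, and the in-text tables are drawn from them. A programmer who follows the shells produces intervals at a level that the protocol does not plan and that disagrees with the in-text tables. A programmer who follows the code produces the planned limits under the wrong label. In addition, the shell listed for Tmax has rows only for Cmax and the AUCs and columns only for geometric means and ratios, so it has no place for a Hodges-Lehmann median difference.

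**Working it through.** **1. Which level the plan's own code gives.** Alpha = 1 − confidence level. For 95%, alpha = 0.05, which matches both code blocks in SAP section 6.5.1. For 90%, alpha = 0.10, which appears nowhere in the analysis text. Protocol section 12.7.3.2 does mention a 90th percentile, but that is a percentile over simulated trials of a 95% interval and does not support a 90% level.

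**2. Intervals affected.** Ratios: 3 parameters × 2 THS variants = 6. Tmax differences: 2. Total: 8.

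**3. Narrowing of the ratio intervals if the shells are followed.** On the log scale the width ratio is t(0.95, df) / t(0.975, df). With complete data and an equal-variance model, 30 subjects × 3 periods = 90 observations, and df = 90 − 30 − 2 − 2 = 56. The planned heterogeneous compound-symmetry model with Kenward-Roger degrees of freedom will give data-dependent values, so a range is shown.

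| df | t(0.95) | t(0.975) | 90% width / 95% width | Narrower by |
|---|---|---|---|---|
| 56 | 1.6725 | 2.0032 | 0.8349 | 16.5% |
| 28 | 1.7011 | 2.0484 | 0.8305 | 17.0% |
| 20 | 1.7247 | 2.0860 | 0.8268 | 17.3% |
| normal limit | 1.6449 | 1.9600 | 0.8392 | 16.1% |

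**4. Illustration on the ratio scale.** Protocol section 12.7.3.1 assumes Cmax geometric means of 12 ng/mL (THS regular) and 14 ng/mL (CIG), so the ratio is 12/14 = 85.71%. The documents give no standard error, so two values are assumed. Limits = 85.71 × exp(± t × SE), df 56.

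| Assumed log-scale SE | 90% interval | 95% interval |
|---|---|---|
| 0.08 | 74.98 to 97.99 | 73.02 to 100.61 |
| 0.20 | 61.35 to 119.76 | 57.42 to 127.95 |

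**5. If the code is run and only the label is wrong.** The limits are at the planned level. A reader who divides the log half-width by the 90% quantile gets SE × 2.0032/1.6725 = SE × 1.198, an overstatement of about 20%.

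**6. Tmax.** The normal approximation gives about 16% narrowing. A simulation of 2,000 untied normal samples gave width ratios of 0.829 (two groups of 30, the form used in the code) and 0.821 (30 pairs), or 17 to 18% narrowing. These figures do not allow for ties (see the objection).

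**The case against.** The planned level is not really in doubt. The protocol rule, the SAP text, both code blocks, the in-text shells and even CPStat2's programmer's note agree on 95%, and SAP section 9 claims alignment with the protocol. The introduction to SAP section 12 says that shells show general layout and may change. On that view a competent programmer would compute 95% and correct the heading, would see from its title that Table 14.2.1.8 needs CPStat2, and would notice any mismatch when the in-text tables are compiled. With no hypothesis, success criterion or significance level, no decision turns on the interval.

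Much of this stands. The intended level can be inferred, the Tmax pointer is an indexing slip, and the error concerns reporting, not the model. In the SE 0.08 example one interval includes 100% and the other does not, but that has no consequence for any study decision.

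The Tmax width figure is also soft. If nominal sampling times are used, which the SAP does not clearly say, Tmax is heavily tied. In a simulation rounded to the sampling grid (assumed medians 7 and 8 minutes, log SD 0.25 to 0.5), the 90% and 95% Hodges-Lehmann intervals coincided in 63 to 92% of runs. For Tmax, too, the suggested code is a two-sample procedure although a signed-rank analysis is planned, so running it fixes the level but not necessarily the interval intended.

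The objection does not remove the need for correction. A confidence level is an analysis specification, not layout, and 90% is written four times across two shells. The SAP offers its code only as one possible implementation and states no precedence over the shells. SAP sections 11 and 12 also rule out manual editing of outputs, so a wrong label has to be put right in the shell or program beforehand.

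**Conclusion.** The concern holds. For all eight THS/CIG intervals the Section 14 shells contradict the protocol, the SAP's analysis section and the in-text tables that cite them, and CPStat2 also contradicts itself. The size depends on what the programmer follows. Computed to the shells, the six ratio intervals are 16.5 to 17.3% narrower on the log scale for degrees of freedom between 56 and 20. Computed by the code, they are correct but mislabelled. For Tmax the difference is about 16 to 18% without ties and may be nil with heavy ties. Point estimates, design and sample size are untouched. The harm is limited to faithful reporting of the planned 95% intervals, but these are the main comparative results, so the shells must be corrected before the tables are produced.

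**What to change.** - In CPStat1, change 90% to 95% in the column heading and the programming note.
- In CPStat2, change 90% to 95% in the column heading and the presentation note. Its programmer's note is already right.
- In the Section 14.2.1 table list, assign CPStat2 to Table 14.2.1.8.
- Optionally, reconcile the p-value column of CPStat1 with ITPStat1, which has none, or label those p-values as nominal, since the protocol sets no significance level.

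The cost is text edits to two shells and one line of the table list. Design, data, model and code do not change.
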